#### **10.3.2.2 Reporting Instructions**

The description of each AE will identify the subject, date of onset, the date of resolution, the severity of the event, the action taken regarding the IMP, the outcome of the event, and the relationship of the event to the IMP.

Standard medical terminology should be used to document AEs. In the case of signs and symptoms, the underlying illness or diagnosis will be recorded as the event when known. For SAEs, a single term for the diagnosis or underlying illness should be recorded on the SAE Report form; in the event this is unknown, the chief sign/symptom making the event serious should be recorded. The terms "death" (an outcome) and "hospitalization" may be used for initial reports only if no further information is available in order to avoid a delay in expedited reporting; however, an adequate follow-up report must follow in which the term "death" or "hospitalization" is replaced by the cause of death or hospitalization.

All IMP-related serious and non-serious AEs must be followed for a final outcome until resolution or stabilization. An outcome of "unknown" is not considered to be an acceptable final outcome. An outcome of not resolved is an acceptable final outcome for non-serious AEs at the end of a subject's participation in a study, and for SAEs at database lock.

#### **10.3.2.2.1 Serious Adverse Event Reporting Instructions**

Serious adverse events require expeditious handling to comply with regulatory requirements. Any SAE occurring in a clinical study subject and follow-up SAE documentation must be reported to the Sponsor's Drug Safety Surveillance Department or designee within 24 hours of the Investigator having knowledge of the SAE.

The Investigator or other qualified individual at the investigative site must complete the SAE form and fax or e-mail it to the Sponsor or designee. **All telephone communication regarding an SAE must be followed by a written report.**

The Investigator is obligated to immediately report to the Sponsor or designee any SAE occurring at any time during the reporting period (Section 10.3.2.1), independent of the circumstances or suspected cause. In addition, the Investigator must promptly report to the Sponsor any SAE occurring at any other time after completion of the study if a causal relationship to IMP is suspected. For all SAEs, the Investigator is obligated to pursue and provide information as requested by the Sponsor in addition to that requested on the SAE form. Information must include a description of the AE in sufficient detail to allow for a complete medical assessment of the case and independent determination of causality. Supporting documentation such as hospital discharge summaries or pertinent laboratory reports should also be sent to the Sponsor. In the case of a subject death, a summary of available autopsy findings must be submitted as soon as possible to the Sponsor. The Investigator will ensure that information reported immediately by telephone or other means and information entered on the SAE form is accurate and consistent.

#### **10.3.2.2.2 Notification of Institutional Review Board or Ethics Committee of Serious Adverse Events**

The Investigator must comply with the applicable regulatory requirements related to the reporting of SAEs to the IRB. The IRB must be informed in a timely manner by the Investigator of SAEs occurring at their site during the study. Investigators must also submit safety information provided by the Sponsor to the IRB as per IRB standard operating procedures.

### **10.3.3 Other Significant Adverse Events**

#### **10.3.3.1 Urgent Safety Measures**

In accordance with the principles of GCP as laid out in ICH E6, the Investigator(s) has/have primary responsibility for assuring subject safety throughout the performance of study procedures. An urgent safety measure is defined as any measure which an Investigator may need to implement which is a deviation from, or a change in, the protocol to eliminate an immediate hazard(s) to trial subjects without prior IRB approval/favorable opinion.

The Investigator may take appropriate urgent safety measures in order to protect the subjects of a clinical trial against any immediate hazards to their health or safety. However, **the Investigator must inform the Sponsor within 24 hours of having taken such measures.**

#### **10.3.3.2 Adverse Events That Qualify as Dose-limiting Toxicity**

**Any AE(s) that qualify as DLT(s) and occur within the DLT evaluation period must be reported to the Sponsor's Medical Monitor via phone contact and also to the Drug Safety Surveillance Department or designee using an SAE form (whether or not the DLT is considered an SAE) within 24 hours of the Investigator having knowledge of the DLT. The appropriate forms must also be completed within 24 hours.**

Refer to the Procedure Manual for reporting instructions.

#### **10.3.3.3 Infusion-related Reactions**

**While all infusion-related reactions should be reported as AEs, and any that additionally meet serious criteria should also be reported to the Sponsor's Drug Safety and Surveillance Department per SAE reporting guidelines, all Grade  $\geq 3$  infusion-related reaction must be reported to the Sponsor's Drug Safety Surveillance Department or designee within 24 hours of the Investigator having knowledge of the event using an SAE form (whether or not the infusion-related reaction is considered an SAE).**

Refer to the Procedure Manual for reporting instructions. The Investigator or designee at the investigative site must complete the SAE form and fax or e-mail it to the Sponsor or designee.

Recommendations for the management of infusion-related reactions are provided in Section [8.2.2](#).

#### **10.3.4 Overdose**

An overdose is defined as the accidental or intentional administration of any dose of an IMP that is > 10% of the appropriate dose. An overdose should be reported, whether or not associated with an AE/SAE, using an SAE form.

#### **10.3.5 Pregnancy Reporting**

Pregnancy in a female trial participant or partner of a male trial participant must be avoided. However, should a pregnancy occur, this process is aimed at ensuring the appropriate monitoring of the potential risk related to IMP exposure of pregnant women and/or fetuses as well as the risks associated with exposure of a father, regarding congenital abnormalities or birth defects in their offspring. It also ensures compliance with applicable international and local regulations. The requirements are applicable to all subjects following exposure to IMP.

**Female trial subjects:** The subject must be advised by the Investigator to inform him/her immediately if she suspects she may be pregnant. The Investigator is obligated to immediately report to the Sponsor or designee any pregnancy occurring at any time after the subject signs the ICF and within 23 weeks after the last dose of IMP.

**Male trial subjects:** The subject must be advised by the Investigator to inform him/her immediately if they suspect their partner became pregnant after the subject was administered IMP. The Investigator is obligated to immediately report to the Sponsor or designee any pregnancy occurring at any time after the subject signs the ICF and within 31 weeks after the last dose of IMP.

When a trial subject reports a pregnancy (post-IMP administration) to the Investigator, IMP should be stopped immediately and a pregnancy test should be arranged for the subject (or their partner) by the Investigator within seven (7) days of the pregnancy being reported.

In the case of pregnancy, The Investigator must immediately notify the Sponsor of this event and report the pregnancy on the Pregnancy Surveillance Form. This includes a study subject as well as the partner of a study subject who becomes pregnant while the subject was receiving IMP. Every attempt will be made to follow the pregnancy to conclusion to obtain information regarding the outcome.

## **11 DATA MANAGEMENT**

### **11.1 Source Data**

Source documents are where data are first recorded, and from which participants' eCRF data are obtained. These include, but are not limited to, hospital records (from which medical history and previous and concurrent medication may be summarized), clinical and office charts, laboratory and pharmacy records, diaries, microfiches, radiographs, and correspondence.

All documents will be stored safely in confidential conditions. The participant will be referred to by the trial participant number/code, not by name, in all data reported to the Sponsor.

### **11.2 Access to Data**

Direct access will be granted to authorized representatives from the Sponsor, Contract Research Organization, host institution and the regulatory authorities to permit trial-related monitoring, audits and inspections. The Investigator(s) must accept that regulatory authorities may conduct an inspection to verify compliance of the study with GCP.

### **11.3 Electronic Case Report Forms**

Subject data will be entered into study eCRFs, in a validated Electronic Data Capture (EDC) system. Management of clinical data will be performed in accordance with applicable industry standards and data cleaning procedures to ensure the integrity of the data. It is the responsibility of the investigative site to prepare and maintain the adequate and accurate eCRFs that have been designed by the Sponsor to record all observations and other data pertinent to the clinical investigation. These eCRFs are organized as an ordered series of electronic data entry modules specific for each scheduled and unscheduled study visit.

Only staff listed on the "Delegation of Authority" page in the study file notebook and who have been appropriately trained to use the EDC system will be issued user identification (ID) allowing them to make entries and edits to the EDC system and to respond to queries. Only the Investigator will be issued a user ID allowing the application of an electronic signature to a completed study subject record signifying the data has been reviewed and verified as complete and accurate.

The Investigator agrees to treat all subject data used and disclosed in connection with this study in accordance with all applicable privacy laws, rules and regulations, including all

applicable provisions of the Health Insurance Portability and Accountability Act and its implementing regulations (“HIPAA”).

The Sponsor or designee will be responsible for the processing and quality control of the data. Data management will be carried out by the Sponsor or designee. The handling of data, including data quality control, will comply with all applicable regulatory guidelines.

Data entry in the electronic data capture system, defined as the clinical database, will be terminated for all subjects and all data (including SAEs and treatment-related AEs), upon written notification by the Sponsor (see Section [9.5](#)).

#### **11.4 Record Keeping and Archiving**

Electronic CRFs, including queries and audit trails, will be retained by the Sponsor or designee. Study data and other essential documents should be retained for a minimum of 2 years after the last approval of a marketing application in an ICH region and until there are no pending or contemplated marketing applications in an ICH region or until at least 2 years have elapsed since the formal discontinuation of clinical development of the investigational product. However, these documents should be retained for a longer period if required by the applicable legal requirements. Kyowa Kirin Pharmaceutical Development, Inc. or its designee will inform the Investigator, in writing, as to when these documents no longer need to be maintained.

All study documentation at the Investigator’s site and Sponsor’s site will be archived in accordance with ICH E6-GCP.

#### **11.5 Study Monitoring**

Study monitoring will be performed in accordance with ICH E6-GCP, the protocol, and applicable local regulations.

### **12 STATISTICAL METHODS AND PLANNED ANALYSIS**

#### **12.1 General Statistical Considerations**

Tabulations of summary statistics, graphical presentations, and statistical analyses will be performed using Statistical Analysis System® software. Descriptive statistics (mean, standard deviation, median, minimum, and maximum) for continuous variables and frequency distributions and percentages for discrete variables will be utilized. All summaries and analyses conducted will be by tumor type, assigned therapy, and combined total subjects. The specifics for these outputs will be described in detail within the Statistical Analysis Plan. The

last pre-administration observation will be used as the baseline value for calculating post-administration changes from baseline. All data entered into the database will be provided in separate data listings showing individual subject values. The planning and reporting of statistical analysis will be carried out as described in the Sponsor's or designee's Standard Operating Procedures governing clinical studies.

## **12.2 Populations to be Analyzed**

The following analysis sets will be used in the study:

- **Safety Analysis Set:** Includes all subjects who receive at least one dose of the investigational product (even a partial dose of either agent).
- **Efficacy Analysis Set:** Includes all subjects who receive combination therapy in Cycle 1 Day 1.
- **Pharmacokinetic Analysis Set:** Includes all subjects who provide at least one post-dose concentration measurement.
- **Pharmacodynamic Analysis Set:** Includes all subjects who provide at least one post-dose sample.

Evaluation of the data for this study will consist primarily of data listings and summary displays. Demographic and other baseline characteristic information will be summarized for the Safety Analysis and Efficacy Analysis Sets. Adverse events will be tabulated by body system, severity, and relation to treatment. Similar presentations will be provided for SAEs, AEs leading to discontinuation of IMP, and AEs leading to death. The tabulation of laboratory parameters will indicate the normal range for each parameter. Each value will be classified as falling above, below, or within the normal range.

### **12.2.1 Subject Disposition**

The number of subjects enrolled, completed, discontinued, and replaced will be presented by dose cohort including the expansion cohorts. A summary of reasons for discontinuation will be provided. The number of subjects in the Safety Analysis and Efficacy Analysis Sets will be summarized as well as the number of subjects in the Safety Analysis Set that were excluded from the Efficacy Analysis Set.

### **12.2.2 Demographic and Baseline Disease Characteristics**

Summaries will include demographics (including age, race, ethnicity, sex, height, weight, and body mass index, physical examination results, ECOG PS, and baseline values for disease-specific measurements (i.e., sum of longest diameters for solid tumors)).

Medical/surgical history, including prior cancer treatments, will be summarized and listed by subject.

### **12.2.3 Prior and Concomitant Medications**

The World Health Organization Drug Dictionary will be used to classify prior and concomitant medications by therapeutic class and preferred term.

### **12.2.4 Investigational Medicinal Product Exposure and Compliance**

Extent of exposure in weeks for each subject for the entire treatment period will be calculated. Extent of exposure, total number of cycles initiated, and total number of doses administered for each investigational product during the treatment period will be summarized.

## **12.3 Efficacy Analysis**

Subjects will be evaluated for tumor response, TTR, DOR, and PFS. The ORR will be calculated as the proportion of subjects in the Efficacy Analysis Set who are responders, i.e., BOR=CR and PR; the 95% exact CI for ORR will be calculated. The ORR will be derived using both the RECIST v. 1.1 and the irRECIST v. 1.1, based on the efficacy evaluable subjects in each expansion cohort for each combination therapy.

The DOR, OS, and PFS will be estimated using the Kaplan-Meier methodology.

### **12.3.1 Sample Size Determination**

The sample size for the dose-finding phase of the study is based on a standard 3+3 dose-finding design and depends on observed toxicity. With 2 doses under consideration, a maximum of 12 subjects will be required.

The Simon's 2-stage optimal design will be used for the expansion cohorts. A cohort may be considered for termination due to lack of efficacy if the observed number of tumor responses (either confirmed or unconfirmed) in the first stage is too small. The characteristics of this design depend on 2 probabilities: the false positive rate (FPR), the probability of declaring the experimental treatment to be superior when in fact it is no better than the historical standard, and the false negative rate (FNR), the probability of concluding the experimental treatment to be no better than the historical standard, when in fact it is superior. The table below presents operating characteristics of the Simon's 2-stage design with 15% FPR and 10% FNR for various expansion cohorts and their historical and target objective response

rates. For example, an initial evaluation of efficacy may be performed after 16 treated subjects with squamous cell NSCLC have evaluable tumor response data. Guided by the Futility Boundary as shown, the decision to terminate the cohort or to allow it to continue will be made after taking into consideration other relevant observations such as duration and depth of response and risk/benefit profile. The number of subjects receiving treatment at the time of the Stage 1 efficacy evaluation may exceed the specified Stage 1 sample size depending on accrual rate, response lag, and other factors.

Upon completion of Stage 1 enrollment for a given cohort, the SRC will review available efficacy and safety data and determine whether enrollment into Stage 2 may continue, even if not all response data are yet available to determine whether the Stage 1 criteria have been met. The SRC may decide that enrollment may continue if the benefit risk assessment is perceived to be positive.

With FPR or one-sided alpha=15% and FNR or 1-power=10%.

**Table 12.3.1-1 Sample Size Estimation by Tumor Type**

Tumor Type	Response Assumptions		Simon 2-Stage Sample Sizes a		Probability of Early Stopping due to Futility (%) if true response rate= Lower Bound
	Lower Bound Historical Response Rate (%)	Target Response Rate (%)	Stage 1 (n1)/Total N	Stage 1 Response Futility Boundary ( $\leq$ ): stop if this many responses or fewer	
NSCLC SQ	20	40	16/32	3	60
NSCLC NSQ PD-L1 non-expressing	10	30	10/21	0	35
Ovarian	10	30	10/21	0	35
CRC (non-MSI high)	5	20	12/29	0	54
SCCHN	25	45	14/36	3	52
HCC	16	36	12/28	6	41
Pancreatic	0	15	15/17	0	>99

a: False positive rate (FPR) or one-sided alpha=15% and false negative rate (FNR) or 1-power=10%.

CRC=colorectal carcinoma; n1=sample size in Stage 1; N=sample size; non-MSI high=non-microsatellite instability high; NSCLC=non-small-cell lung cancer; NSQ=non-squamous; PD-L1=programmed cell death-ligand 1; HCC=hepatocellular carcinoma; SOC=Standard of care; SCCHN=squamous cell carcinoma of the head and neck. SQ=squamous.

A maximum of 188 subjects will participate in the study.

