#### **8.1.2.1 Dose Reduction**

There will be no intra-patient dose reduction of either IMP by the Investigator. Doses within an assigned cohort may only be changed at the discretion of the SRC. (As of Amendment 3, the SRC will be disbanded.)

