1 INTRODUCTION

This Statistical Analysis Plan (SAP) has been developed after review of Kyowa Kirin Pharmaceutical Development, Inc. Protocol 0761-014 (Amendment 2, dated 05 Dec 2016), along with the corresponding electronic case report forms (eCRF). This SAP describes the analysis sets and specific details for the statistical methods to be used for the analysis and reporting of all efficacy, safety, pharmacokinetic parameters, and immunogenicity data collected during the conduct of Protocol 0761-014. This SAP supersedes the statistical considerations identified in Protocol 0761-014 with regards to details of the analyses; where considerations are substantially different, they will be identified as such in this document. In the event that the protocol has amendment(s) that do not have an impact on the statistical analysis methodology, this SAP will not require an amendment. This SAP has been developed and finalized prior to database lock of the clinical database for Protocol 0761-014. If additional analyses are required to supplement the planned analyses described in this SAP, they may be performed and will be identified in the Clinical Study Report (CSR).

This SAP is being written with consideration of the recommendations outlined in the International Conference on Harmonization (ICH) E9 Guideline entitled “Guidance for Industry: Statistical Principles for Clinical Trials” and the most recent ICH E3 Guideline, entitled “Guidance for Industry: Structure and Content of Clinical Study Reports.”

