	Lower Bound Historical Response Rate (%)	Target Response Rate (%)	Stage 1 (n1)/ Total (N)	Stage 1 Response Futility Boundary (≤): Stop if this many responses or fewer	
NSCLC SQ	20	40	16/32	3	60
NSCLC NSQ PD-L1 non-expressing	10	30	10/21	0	35
Ovarian	10	30	10/21	0	35
CRC (non-MSI high)	5	20	12/29	0	54
SCCHN	25	45	14/36	3	52
HCC	16	36	12/28	1	41
Pancreatic	0	15	15/17	0	>99

a: False positive rate (FPR) or one-sided alpha=15% and false negative rate (FNR) or 1-power=10%.

CRC=colorectal carcinoma; n1=sample size in Stage 1; N=sample size; non-MSI high=non-microsatellite instability high; NSCLC=non-small-cell lung cancer; NSQ=non-squamous; PD-L1=programmed cell death-ligand 1; HCC=hepatocellular carcinoma; SCCHN=squamous cell carcinoma of the head and neck; SQ=squamous.

A maximum of 188 subjects will participate in the study. This number takes into account a total of 4 subjects that were enrolled in the dose-finding stage and a total of 184 subjects (across all tumor types) calculated for the expansion cohort.

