4.9.2.2 Interim Analyses and Data Monitoring

Safety information will be monitored on a continuing basis to support decisions regarding dose finding in Phase 1 and cohort expansion in Phase 2. Guided by Simon's 2-stage design, tumor response rates together with other relevant observations such as duration and depth of response will be evaluated after Stage 1 enrollment is complete; these results will be reviewed by the SRC as a basis for benefit risk assessment and decisions regarding Stage 2 enrollment. The assumed historic and target response rates at the time of protocol finalization may have been changed over time and may need to be adjusted by the time of the data evaluation.

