Continue with Expansion phase (Mogamulizumab x mg/kg + Nivolumab 240 mg).			

Programming note: Print a cover page for this listing where all inclusion and exclusion criteria (Full text) will be printed. In the body of the listing, only the numbers for the criteria will be displayed. The cover page for the listing contains the following information with the following template.

Protocol Version	Additional No.	Additional Criteria Description	Category	No.	Criteria
Amendment 1			INCLUSION	I01	Subject is age 18 years or older

Listing 16.2.3
Analysis Population

Treatment = Phase 1: Dose finding phase (Mogamulizumab 1 mg/kg + Nivolumab 240 mg)

Subject	Cancer Type	Excluded from Analysis Set	Reasons for Exclusion from Analysis Set
xxx-xxx	Liver	Safety	xxxxxxxxxxxxxxxxxxxxxxxxxxxxxxxx
xxx-xxx	Renal Cell	Efficacy	xxxxxxxxxxxxxxxxxxxxxxxxxxxxxxxx
xxx-xxx	Sarcoma	Pharmacokinetic	xxxxxxxxxxxxxxxxxxxxxxxxxxxxxxxx

Continue Expansion phase (Mogamulizumab x mg/kg + Nivolumab 240 mg).

Note: all enrolled subjects were treated and included in both safety analysis set and efficacy analysis set.

Listing 16.2.4.1
 Demographics

Treatment = Phase 1: Dose finding phase (Mogamulizumab 1 mg/kg + Nivolumab 240 mg)

Subject	Cancer Type	Age (yrs) [1]	Gender	Child-bearing potential [2]	Race	Ethnicity	Height (cm)	Baseline Weight (kg) [3]	Tobacco Use	# of Pack-Years
xxx-xxx	Liver	xx	Male		xxxxxxxxxx	xxxxxxx	xxx	xxx.x		
	Renal Cell	xx	Female	No	Other:	xxxxxxxxxx	xxx	xxx.x		
xxx-xxx					xxxxxxxxxx					
xxx-xxx	Sarcoma	xx	Male		xxxxxxxxxx	xxxxxxx	xxx	xxx.x		
xxx-xxx	Other: xxxx	xx	Male		xxxxxxxxxx	xxxxxxx	xxx	xxx.x		

Continue with Expansion phase (Mogamulizumab x mg/kg + Nivolumab 240 mg).

[1] Age at informed consent.

[2] For Female only.

[3] Baseline is defined as the last measurement obtained prior to the first dose of the study drug.

Listing 16.2.4.2
Cancer Disease History

Treatment = Phase 1: Dose finding phase (Mogamulizumab 1 mg/kg + Nivolumab 240 mg)

Subject	Cancer Type	Location of Primary Tumor	Date of Initial Diagnosis (Months [1])	Date of First Recurrence or Local Advancement (Months [1])	Date of First Presentation with Distant Metastatic Disease (Months [1])	Stage at Enrollment	ECOG	EGFR Mutation	ALK Rearrang- ement	HPV Infection	MSI (Assay: Result)
xxx-xxx	Liver	xxx	YYYY-MM-DD (xx)		YYYY-MM-DD (xx)	Metastatic	x	xxx	xxx	xxx	xxx
xxx-xxx	Renal Cell	xxx	YYYY-MM (xx*) YYYY-MM-DD		YYYY-MM-DD (xx)	Metastatic	x	xxx	xxx	xxx	xxx

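### HCC Stage 1 futility boundary is 6 of 12 in the protocol and 1 of 12 in the SAP; only 1 fits the 41% early-stopping probability printed in both

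*Protocol*

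**What the plan says.** Protocol 12.3.1 and SAP 4.2 both use a Simon optimal two-stage design for each expansion cohort, with one-sided alpha 15% and power 90%. Each prints a table of historical rate, target rate, Stage 1 and total sample sizes, Stage 1 futility boundary, and early-stopping probability when the true rate equals the historical rate.

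- Protocol Table 12.3.1-1, HCC: "HCC 16 36 12/28 6 41"
- SAP 4.2 Table 1, HCC: "HCC 16 36 12/28 1 41"

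The boundary column is defined in the protocol header as "stop if this many responses or fewer". Every other cell of the HCC row, and all six other rows, agree between the two tables.

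The boundary is guidance. Protocol 12.3.1 says "Guided by the Futility Boundary as shown, the decision to terminate the cohort or to allow it to continue will be made" with other evidence also weighed, including how long and how deep responses are and the balance of risk and benefit. SAP 4.9.2.2 says of the Stage 1 results that "these results will be reviewed by the SRC as a basis for benefit risk assessment and decisions regarding Stage 2 enrollment".

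SAP Section 1 says the SAP supersedes the protocol's statistical considerations "with regards to details of the analyses; where considerations are substantially different, they will be identified as such in this document". Nothing in SAP 4.2 mentions the HCC boundary.

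**The concern.** One design cannot have two Stage 1 boundaries. With 2 to 6 responses among the first 12 HCC subjects, the protocol's table points to stopping and the SAP's to continuing. If the combination works as targeted, that range is by far the likeliest Stage 1 result.

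The protocol's value is also implausible in itself. With a boundary of 6, HCC would need 7 of 12 responses (58%) to continue, although its target is 36%. It would be the only cohort whose minimum rate to continue exceeds its own target.

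What remains at stake is mainly the record. Protocol 8.1.2.1 says "As of Amendment 3, the SRC will be disbanded" (the SRC is the Safety Review Committee), and a footnote in the shell of SAP Listing 16.2.3 already states that "all enrolled subjects were treated and included in both safety analysis set and efficacy analysis set". The HCC Stage 1 decision has therefore probably been made. The SAP plans no table giving the Stage 1 count or the boundary consulted. Its best-overall-response tables count confirmed responses only, while the Stage 1 rule also counts unconfirmed ones.

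**Working it through.** **Inputs.** From the HCC row of both tables: historical rate p0 = 0.16, target p1 = 0.36, n1 = 12, N = 28, early stopping at p0 = 41%. Boundary r1 = 6 (protocol) or 1 (SAP). Alpha 15% one-sided and power 90% come from the table footnotes.

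**Step 1: reproduce the printed 41%.** The early-stopping probability is P(X ≤ r1) for X ~ Binomial(12, 0.16).

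- r1 = 0: 0.84^12 = 0.123
- r1 = 1: 0.123 + 12 × 0.16 × 0.84^11 = 0.123 + 0.282 = 0.405
- r1 = 2: 0.701
- r1 = 6: 0.999

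Only r1 = 1 gives 41%. The nearest alternatives give 12.3% and 70.1%.

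**Step 2: apply the same formula to all rows**, at the historical rate and at the target.

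| Cohort | r1/n1 | Stop at historical rate (printed) | Stop at target | Minimum rate to continue vs target |
|---|---|---|---|---|
| NSCLC SQ | 3/16 | 59.8% (60) | 6.5% | 25% vs 40% |
| NSCLC NSQ and ovarian | 0/10 | 34.9% (35) | 2.8% | 10% vs 30% |
| CRC | 0/12 | 54.0% (54) | 6.9% | 8% vs 20% |
| SCCHN | 3/14 | 52.1% (52) | 6.3% | 29% vs 45% |
| Pancreatic | 0/15 | 100% (>99) | 8.7% | 7% vs 15% |
| HCC, SAP | 1/12 | 40.5% (41) | 3.7% | 17% vs 36% |
| HCC, protocol | 6/12 | 99.9% (41) | 90.3% | 58% vs 36% |

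The method reproduces every printed figure except the protocol's HCC row.

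**Step 3: search for the optimal design.** An exhaustive search for 16% vs 36% with alpha ≤ 0.15 and power ≥ 0.90, minimising expected sample size at p0, returns r1/n1 = 1/12 and r/N = 6/28. Its alpha is 13.9%, its power 90.5%, and its expected size at p0 is 12 + (1 − 0.4055) × 16 = 21.5. The same search returns the printed n1, r1 and N for NSCLC SQ (16, 3, 32), NSCLC NSQ and ovarian (10, 0, 21), CRC (12, 0, 29) and SCCHN (14, 3, 36).

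The final cut-off for HCC is 6 of 28, so the protocol may have printed the final cut-off in the Stage 1 column. That is an inference, because neither table shows final cut-offs.

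**Step 4: effect of using 6 as printed.**

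- Power ceiling: P(X ≥ 7) for Binomial(12, 0.36) = 1 − 0.903 = 9.7%, whatever the final cut-off, because a cohort that stops cannot succeed.
- Zone of conflict, P(2 ≤ X ≤ 6): at 36%, 0.9030 − 0.0366 = 86.6%; at 16%, 0.9990 − 0.4055 = 59.4% (from unrounded values).

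**The case against.** The strongest reply is that the 90.3% and 9.7% describe a rule nobody had to follow mechanically. A cohort was only to be considered for termination, the SRC weighed other evidence, and it could let enrollment continue before all Stage 1 responses were in. The misprint also contradicts the 41% beside it, and nothing shows that anyone used 6. This stands as a limit on the practical harm. It does not reconcile the tables, and the boundary shown in the protocol is 6.

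A second reply is that the SAP governs. Its supersession clause could reasonably be read to make 1 the operative value at analysis. The clause is limited to details of the analyses, however, and the Stage 1 boundary guides an enrollment decision made during the trial. The SAP also names protocol Amendment 2 as its source, while the protocol at hand carries Amendment 3 text. If Amendment 2 printed 1, the SAP's author had no difference to flag. The SAP's silence should therefore not be counted as a fault; a clarifying sentence is still needed.

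Third, part of the Stage 1 result could be rebuilt from the subject-level responses and image dates in Listing 16.2.6.1 and the HCC enrollment in Table 14.1.1.2, and protocol 12.10 already requires departures from the planned statistics to be described in the CSR. That is fair. What cannot be rebuilt is which boundary the SRC had in front of it.

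Finally, the 6 could be an error in reading the PDF. Its match with the design's final cut-off makes a genuine slip more likely, but the cell should be checked against the source file.

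**Conclusion.** The concern holds. The two tables conflict on the HCC Stage 1 boundary, and the protocol's own sample sizes, early-stopping probability and error rates require 1. This needs no outside source and no assumption beyond exact binomial probabilities for 12 subjects.

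The consequence is conditional. Stopping 90.3% of the time at target, and the power ceiling of 9.7%, follow only if 6 was applied as printed to exactly 12 evaluable subjects; protocol 12.3.1 allows more than the planned number to be under treatment at the Stage 1 evaluation. With 1 and the inferred final cut-off of 6 of 28, the design has alpha 13.9% and power 90.5%, in line with the stated 15% and 90%. That the decision is already past is likely but rests on indirect evidence. This should be fixed: it is a wrong decision threshold with a large effect on the design's properties, softened by its advisory status.

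**What to change.** 1. In protocol Table 12.3.1-1, after checking the source file, change the HCC Stage 1 boundary from 6 to 1, by clarification letter or in the next amendment.
2. In SAP 4.2, add one sentence saying that the HCC boundary of 1 differs from the 6 printed in the protocol and that 1 is the value consistent with 41%.
3. In the CSR, report the HCC Stage 1 response count (confirmed plus unconfirmed), the number of subjects it was based on, the boundary that guided the decision, and the reason for the decision. This matters most if 2 to 6 subjects responded.

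The cost is one table cell, one SAP sentence and a short CSR paragraph. No new data or analysis is needed. If the decision is indeed past, the CSR paragraph is the part with practical value; the other two changes set the record straight.
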